Records AEs and concomitant medications	X	X	X	X	X	X	X	X	X	X	X	X	X
Assess adherence to the OBR		X						X					
BLOOD ² AND/OR URINE SAMPLES TO BE COLLECTED BEFORE STUDY DRUG ADMINISTRATION													
Hepatitis serology, C-reactive protein													
Hematology, serum chemistry, urinalysis (see Section 7.2.2)								X					
Archive sample								X					
Serum for pregnancy test for females of childbearing potential													
Urine for pregnancy test for females of childbearing potential		X		X		X		X		X		X	
HIV-1 RNA (viral load)		X						X					
HIV-1 viral resistance sample ³		X						X					
CD4 ⁺ T-cell count ⁴		X						X					
Immunogenicity of ibalizumab (2 tubes x 3 mL each) ⁴								X					
STUDY DRUG ADMINISTRATION AND AFTER													
Administer study medication ⁵	X	X	X	X	X	X	X	X	X	X	X	X	X
Record vital sign measurements and AEs after infusion	X	X	X	X	X	X	X	X	X	X	X	X	X

Table 3-6. Schedule of Events: Cohort 2, Week 4 through end of study (Continued)

Week	Study Visit								
	132	134	136	138	140	142	144/ EOS	150/ Follow up	Early Withdrawal ⁶
Visit window (days)	±2	±2	±2	±2	±2	±2	±2	±2	
ACTIVITIES TO BE COMPLETED BEFORE STUDY DRUG ADMINISTRATION									
Record results of a complete physical examination							X	X	X
Record results of an abbreviated physical examination ¹									
Record the patient's weight							X	X	X
Record vital sign measurements	X	X	X	X	X	X	X	X	X
Records AEs and concomitant medications	X	X	X	X	X	X	X	X	X
Assess adherence to the OBR	X						X	X	X
BLOOD ² AND/OR URINE SAMPLES TO BE COLLECTED BEFORE STUDY DRUG ADMINISTRATION									
Hepatitis serology, C-reactive protein								X	X
Hematology, serum chemistry, urinalysis (see Section 7.2.2)								X	X
Archive sample							X	X	X
Serum for pregnancy test for females of childbearing potential									X
Urine for pregnancy test for females of childbearing potential	X		X		X		X	X	
HIV-1 RNA (viral load)	X						X	X	X
HIV-1 viral resistance sample ³	X						X	X	X
CD4 ⁺ T-cell count ⁴	X						X	X	X
Immunogenicity of ibalizumab (2 tubes x 3 mL each) ⁴							X	X	X
STUDY DRUG ADMINISTRATION AND AFTER									
Administer study medication ⁵	X	X	X	X	X	X	X		
Record vital sign measurements and AEs after infusion	X	X	X	X	X	X	X		

- ¹ Abbreviated physical examination includes examination of lymph nodes, respiratory and cardiovascular systems, abdomen, extremities, and nervous system.
- ² Patients need not fast before blood sampling.
- ³ Viral resistance testing will include assessments of reverse transcriptase, protease, integrase, and envelope (entry) genes and chemokine coreceptor utilization; the samples will be collected and stored, and testing will only be performed for patients who experience virologic failure while on the study.
- ⁴ Samples are to be drawn within 1 hour before the start of the infusion (if infusion is scheduled for that visit).
- ⁵ All patients in Cohort 2 must be observed for 1 hour after the completion of study drug administration. If the patient does not experience an AE(s) related to the infusion (local or systemic) through and including the second infusion on Day 14, then the observation time can be reduced to 15 minutes thereafter.
- ⁶ Patients who withdraw or are withdrawn at any time prior to the Week 102 visit should have Early Withdrawal procedures performed.

Abbreviations: AE = adverse event; ART = antiretroviral therapy; CD4⁺ = helper T-cell; EOS = end of study; FSH = follicle-stimulating hormone; HIV = human immunodeficiency virus; OBR = optimized background regimen

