Record vital sign measurements and AEs and observe (15 min.) after infusion	X	X	X	X	X	X	X	X	X	X	X	X	X

Table 3-2. Schedule of Events: Cohort 1 – 800 mg every 2 weeks, Week 6 through end of study (Continued)

Week	Study Visit								
	132	134	136	138	140	142	144/ EOS	150/ Follow up	Early Withdrawal ⁵
Visit window (days)	±2	±2	±2	±2	±2	±2	±2	±2	
ACTIVITIES TO BE COMPLETED BEFORE STUDY DRUG ADMINISTRATION									
Record results of a complete physical examination							X	X	X
Record results of an abbreviated physical examination ¹									
Record the patient's weight							X	X	X
Record vital sign measurements	X	X	X	X	X	X	X	X	X
Records AEs and concomitant medications	X	X	X	X	X	X	X	X	X
Assess adherence to the OBR	X						X	X	X
BLOOD ² AND/OR URINE SAMPLES TO BE COLLECTED BEFORE STUDY DRUG ADMINISTRATION									
Hepatitis serology, C-reactive protein								X	X
Hematology, serum chemistry, urinalysis (see Section 7.2.2)								X	X
Archive sample							X	X	X
Serum for pregnancy test for females of childbearing potential									X
Urine for pregnancy test for females of childbearing potential	X		X		X		X	X	
HIV-1 RNA (viral load)	X						X	X	X
HIV-1 viral resistance sample ³	X						X	X	X
CD4 ⁺ T-cell count ⁴	X						X	X	X
Immunogenicity of ibalizumab (2 tubes x 3 mL each) ⁴							X	X	X
STUDY DRUG ADMINISTRATION AND AFTER									
Administer study medication	X	X	X	X	X	X	X		
Record vital sign measurements and AEs and observe (15 min.) after infusion	X	X	X	X	X	X	X		

- ¹ Abbreviated physical examination will include an examination of lymph nodes, respiratory and cardiovascular systems, abdomen, extremities, and nervous system.
- ² Patients need not fast before blood sampling.
- ³ Viral resistance testing will include assessments of reverse transcriptase, protease, integrase, and envelope (entry) genes and chemokine coreceptor utilization; the samples will be collected and stored, and testing will only be performed for patients who experience virologic failure while on the study.
- ⁴ Samples to be drawn within 1 hour before the start of the infusion (if infusion is scheduled for that visit).
- ⁵ Patients who withdraw or are withdrawn at any time prior to the Week 150 visit should have Early Withdrawal procedures performed.

Abbreviations: AE = adverse event; ART = antiretroviral therapy; CD4⁺ = helper T-cell; EOS = end of study; FSH = follicle-stimulating hormone; HIV = human immunodeficiency virus; OBR = optimized background regimen

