4.4 Missed Doses of Study Drug

4.4.1 Cohort 1

Patients should receive study drug per the Schedule of Events (Section 3.4). A missed dose is defined as any dose of study drug that is not administered within the study visit window. Patients who miss doses of study medication for two consecutive dosing intervals (i.e., >28 days without a study drug infusion) of 800 mg dosage or one and one-half dosing intervals (i.e., >42 days without a study drug infusion) of the 2,000 mg dose may be withdrawn from the study.

Missed Doses. If a dose is missed, the missed dose should be administered at the first opportunity. If an 800 mg dose is missed and cannot be administered at least 3 days before the next scheduled dose, it should be skipped. If a 2,000 mg dose is missed and cannot be administered at least 5 days before the next scheduled dose, it should be skipped.

End of study (EOS) procedures should be performed as soon as possible after the patient qualifies for withdrawal due to missed doses. Patients who are withdrawn from the study for missed doses may not be permitted to participate in other ibalizumab protocols.

4.4.2 Cohort 2

Patients should receive study drug per the Schedule of Events (Section 3.4). A missed dose is defined as any dose of study drug that is not administered within the study visit window. Patients who miss doses of study medication for two consecutive dosing intervals (i.e., >28 days without a study drug infusion) or miss greater than two doses cumulatively will be withdrawn from the study. EOS procedures should be performed as soon as possible after the patient qualifies for withdrawal due to missed doses. Patients who are withdrawn from the study for missed doses may not be permitted to participate in other ibalizumab protocols.

Missed Initial (Loading) Dose. If the initial 2,000 mg dose (loading dose) of study drug is administered outside the treatment window, the dose should be administered at the first available opportunity and the timing of subsequent doses should be adjusted to coincide with the actual administration time of the first dose.

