5.3.2 Handling Withdrawals and Discontinuations

Patients are free to withdraw from the study at any time upon request. Patient participation in the trial may be stopped at any time at the discretion of the investigator or at the request of the Sponsor or designee. At the time of withdrawal or discontinuation, the investigator will assess the best options for treatment and discuss these options with the patient.

When a patient withdraws or is discontinued from the study, the reason(s) for withdrawal or discontinuation will be recorded by the investigator. Whenever possible, all patients who withdraw, or are discontinued from the study prematurely, will undergo all Early Withdrawal procedures as described in the Schedule of Events in Section 3.4. Patients who fail to return for final assessments will be contacted by the site personnel in an attempt to have the patients comply with the protocol. A minimum of two documented phone calls should be made over the course of at least 2 weeks. If the site personnel receive no response, they should send a certified letter requesting that the patient contact the site regarding their status in the study. If the patient does not respond at this point, the date the certified letter was mailed will be considered the date of study withdrawal.

In the event of a patient death during the study, the date of death (as listed on the death certificate) will be used for the date of study discontinuation.

It is vital to obtain follow-up data on any patient withdrawn because of an AE or SAE. In such cases, the patient will be followed to satisfactory resolution or until the Principal Investigator deems the event to be chronic or the patient to be stable. In any case, every effort must be made to undertake protocol-specified safety follow-up procedures.

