- Record vital sign measurements after completion of infusion and observe patient for at least 15 minutes
- Record AEs

6.3 Cohort 2

Patients will complete all Screening procedures during the 6 weeks before Day 0/Baseline. Successful Screening results will allow the patients to proceed to the Day 0/Baseline visit, where they will initiate the selected OBR in addition to undergoing physical and laboratory measures as specified in the Schedule of Events (see Table 3-5). At this visit, patients will also receive the loading dose of the study medication (2,000 mg). Patients will return to the clinic on Day 7 for effectiveness and safety evaluations and on Day 14 and every 2 weeks thereafter through the remainder of participation in the study for study drug administration (800 mg) and effectiveness and safety evaluations. Patients who are discontinued or who withdraw from the study prematurely will be asked to return for an Early Withdrawal visit to complete all assessments for that visit, as detailed in the Schedule of Events.

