6.4 Early Withdrawal Procedures

Patients who withdraw from the study at any time before Week 96/EOS will be asked to complete all Early Withdrawal procedures to ensure safety and collect as much effectiveness data as possible.

The following procedures will be completed at the Early Withdrawal visit (study drug is not administered at Early Withdrawal):

- Record results of a complete physical examination
- Record the patient's weight
- Record vital sign measurements

- Record AEs and concomitant medications
- Assess adherence to the OBR
- Collect blood and/or urine samples for the following:
 - Hepatitis serology and C-reactive protein
 - Clinical laboratory assessments (serum chemistry, hematology, and urinalysis; see [Section 7.2.2](#) for a complete list of parameters)
 - Archive sample
 - Serum pregnancy test for females of childbearing potential
 - HIV-1 RNA (viral load)
 - HIV-1 viral resistance sample (will be stored for later use if needed)
 - CD4⁺ cell count
 - Immunogenicity of ibalizumab

6.5 **Unscheduled Visits**

Unscheduled visits are allowed for the following reasons:

- To perform a confirmatory plasma viral load determination
- To perform confirmatory laboratory testing for clinically abnormal values
- Any time the investigator feels that they are clinically required for safety reasons related to the patient's participation in this trial

Findings during these unscheduled visits must be reported in the EDC system under the unscheduled visit section.

7. Study Assessments

A central laboratory will analyze all blood and urine samples with the exception of the HIV-1 resistance testing and immunogenicity testing, which will be undertaken by appropriate specialty contract laboratories. Urine samples will be analyzed at the site; if abnormal results are obtained for a patient, a urine sample will be sent to the central laboratory for microscopic evaluation.

The following assessments will be conducted at the times indicated in the Schedule of Events (Tables 3-1 through 3-6).

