#### Listing 16.2.6.2 CD4+ Cell Count (cells/mm^3)

# Unimputed Original Values Imputed with LOCF [5]

Treatment	Patient ID	Visit [1]	Visit Date (Study Day)	CD4+ Cell Count (cells/mm^3) [2]	CD4+ Cell Count Change from Baseline (%)	Toxicity [4]	CD4+ Cell Count (cells/mm^3) [2]	CD4+ Cell Count Change from Baseline (%)
C1:301/800mg	311-XX-XXX	XXXXXXX	DDMONYYYY (XX)	XXX*	XXXX	XXXX	XXX*	XXXX
C2:800mg	311-XX-XXX	XXXXXXX	DDMONYYYY (XX)	XXX	XXXX	XXXX	XXX	XXXX

[1] EOS=End of Study visit conducted at Week 174 (for TMB-301 rollovers)/Week 150 (for all other patients).

[2]\*=below 200 cells/mm^3

[3] Calculated as (visit value - baseline)/baseline\*100%

[4]Toxicity is defined as 2 consecutive laboratory results, at least 14 days apart, with a CD4+ cell count below 200 cells/mm3 that also represents a 50% reduction from the baseline CD4+ cell count.

[5] Missing values are imputed using the Last Observation Carried Forward (LOCF) method.e

Westat (Created on DDMMMYYYY)
S:\TMB311\DA\SAS\L\_CD4.SAS

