 For TMB301 Rollovers, BASELINE is the value recorded on Day 7 of the TMB-301 study. For TMB202 Rollovers, BASELINE is the value recorded on Day 0 of the TMB-202 study. Lab samples were not collected at the TMB-311 Screening for the Cohort 1 patients. EOS=End of Study visit conducted at Week 96.

 $\label{lem:westat} \begin{tabular}{ll} $\tt Created on DDMMYYYY) \\ {\tt S:\TMB311\DA\SAS\L\_LABOTH.SAS} \end{tabular}$ 

 L = Below lower limit of normal; H = Above upper limit of normal.

 Potentially Clinically Significant is defined as having a result either below the lower limit of normal or above the upper limit of normal.

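### The protocol contradicts itself on which assessments a withdrawing patient has, so a site could omit exit safety laboratory tests

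*Protocol*

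**What the plan says.** **Cut-offs.** The Cohort 1 schedules (Tables 3-2 and 3-4, footnote 5) say: "Patients who withdraw or are withdrawn at any time prior to the Week 150 visit should have Early Withdrawal procedures performed". The Cohort 2 schedule (Table 3-6, footnote 6) says: "Patients who withdraw or are withdrawn at any time prior to the Week 102 visit should have Early Withdrawal procedures performed". Protocol Section 6.4, which is not limited to a cohort, says: "Patients who withdraw from the study at any time before Week 96/EOS will be asked to complete all Early Withdrawal procedures".

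**Rules without a cut-off.** Section 5.3.2 says that, whenever possible, "all patients who withdraw, or are discontinued from the study prematurely, will undergo all Early Withdrawal procedures", and refers to the Schedule of Events for what those are. The introduction to Section 6.2 says "Patients who are discontinued or who withdraw from the study prematurely will be asked to return for an Early Withdrawal visit", and the introductions to 6.1 and 6.3 say the same. SAP Section 2.1 repeats it.

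**Missed doses.** For patients withdrawn for missed doses, Section 4.4.1 names a different procedure set: "EOS) procedures should be performed as soon as possible after the patient qualifies for withdrawal due to missed doses". Section 4.4.2 repeats this for Cohort 2.

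**Meaning of EOS.** The schedules put EOS at Week 144, with follow-up at Week 150. Section 6.4 attaches the label to Week 96, and a note in Section 4.4.2 attaches it to Week 102. Section 6.3.7 is headed Week 150 but names Week 102 in its first line. In the SAP, Section 3.3.1 uses Week 144. The footnote to mock Listing 16.2.6.2 (CD4+) has "EOS=End of Study visit conducted at Week 174 (for TMB-301 rollovers)/Week 150 (for all other patients", and the footnote to a mock laboratory listing has "EOS=End of Study visit conducted at Week 96".

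**The concern.** Safety and tolerability are primary objectives in both cohorts, and clinical laboratory parameters are a named safety assessment (Section 3.6). Patients who leave early are often those whose safety data matter most, and an exit sample that is not drawn cannot be recovered at analysis.

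Two problems arise. First, dosing continues to Week 144, yet the Cohort 2 footnote and Section 6.4 attach the exit visit only to departures before Week 102 or Week 96. Second, missed-dose withdrawals are sent to a procedure set that, in its Week 144 column, lacks the safety laboratory tests that other withdrawals have. For Cohort 2, Section 4.4.2 makes withdrawal mandatory once the missed-dose criterion is met, so sites will have to apply this route. What is collected then depends on which section the site consults.

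**Working it through.** There is no planned figure to reproduce. The check compares the passages and does simple arithmetic on visit weeks.

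**1. The rules side by side**

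| Source | Applies to | Early Withdrawal procedures for exits |
|---|---|---|
| Tables 3-2 and 3-4, footnote 5 | Cohort 1 | before Week 150 |
| Table 3-6, footnote 6 | Cohort 2 | before Week 102 |
| Section 6.4 | all patients | before Week 96 (called EOS) |
| Section 5.3.2 | all patients | any premature exit, where possible |
| Sections 6.1, 6.2, 6.3 (introductions) | each cohort | any premature exit |
| Sections 4.4.1, 4.4.2 | missed-dose withdrawals | EOS procedures named instead |

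Take an exit at Week 110. In Cohort 1, footnote 5 asks for the visit and Section 6.4 does not. In Cohort 2, neither footnote 6 nor Section 6.4 asks for it. In both cohorts the general rules do. No patient faces all three cut-offs: Cohort 1 faces 150 and 96, Cohort 2 faces 102 and 96.

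**2. Size of the window that the narrower cut-offs leave out** (last dose at Week 144)

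- Footnote 6: 144 − 102 = 42 weeks; 42/144 = 29%.
- Section 6.4: 144 − 96 = 48 weeks; 48/144 = 33%.
- Cohort 1 footnotes: 0 weeks.

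**3. Whether routine tests fill the gap.** After Week 96, hematology, chemistry and urinalysis are scheduled only at Weeks 120 and 150 in every schedule. The gaps are 120 − 96 = 24 weeks and 150 − 120 = 30 weeks. A patient who left without the exit visit could have safety laboratory results up to about 24 weeks old just before Week 120, or about 30 weeks old just before Week 150.

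**4. What EOS procedures would contain** (Table 3-6 columns)

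| Item | Week 144/EOS | Early Withdrawal | Week 96 | Week 102 |
|---|---|---|---|---|
| Hematology, chemistry, urinalysis | no | yes | yes | no |
| Hepatitis serology, C-reactive protein | no | yes | yes | no |
| Pregnancy test | urine | serum | serum | none |
| Viral load, resistance, CD4+, immunogenicity | yes | yes | yes | no |
| Study drug row | yes | no | yes | yes |

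On the Week 144 reading, a missed-dose withdrawal lacks the safety laboratory tests, hepatitis serology and C-reactive protein. On the Week 102 reading no blood or urine sample is required. On the Week 96 reading the full set is. Section 7.2.5 also calls for a serum pregnancy test at EOS, where the Week 144 column shows urine. The Week 144/EOS column includes study drug administration, whereas Section 6.4 states that none is given at Early Withdrawal.

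**The case against.** The strongest reply is that Sections 5.3.2 and 6.1 to 6.3, supported by SAP Section 2.1, already ask for Early Withdrawal procedures after any premature exit, and that nothing forbids them after Week 96 or 102. The reference in 5.3.2 to the Schedule of Events can be read as saying what the procedures are, not who has them. This stands in part: it rules out saying that the tests are not required. But no text says which rule governs, the cut-offs are explicit, and Section 4.4 is the more specific instruction for missed doses.

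It can also be said that adverse events are recorded until 30 days after the last dose whatever the cut-off (Section 8.3), that exits due to adverse events carry their own follow-up duty (Section 5.3.2), and that the Day 7 endpoint is untouched. This stands and limits the severity. Section 8.2 does, however, count clinically significant laboratory findings among the sources of adverse events, and these need a sample.

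A reader might infer more than the documents support:

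- **That missed-dose exits always lose the safety tests.** This fails if EOS is read as Week 96, and those patients also fall under the general withdrawal rules.
- **That a Cohort 2 patient leaving late in dosing has had no laboratory test since Week 120.** Viral load, resistance and CD4+ samples are scheduled at Week 132. The long gap in hematology and chemistry is also part of the routine schedule for patients who stay.
- **That early exits will be mixed into the SAP's 144/EOS summaries.** SAP Section 3.3.1 uses the nominal visit, but it ties Week 144/EOS to the Day 0 date with a 2-day window. The virologic-outcome listing says visits are assigned by study day, and the schedule has a separate Early Withdrawal column. Nothing shows that an exit would be entered as EOS. The conflicting SAP labels are footnotes to mock listings, whose general notes describe displayed visit names as examples.

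**Conclusion.** The contradiction is real and should be fixed. The narrower cut-offs leave 29% (Cohort 2 table) or 33% (Section 6.4) of the dosing weeks without an Early Withdrawal instruction in those passages, and the missed-dose sections point to a set whose Week 144 column lacks safety laboratory tests. The instructions conflict, so the loss of exit safety tests is possible, not certain. Under the Week 144 column, viral load, resistance, CD4+ and immunogenicity samples are kept.

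The percentages count dosing weeks to Week 144 and describe the span of the rules, not the share of patients. The number affected cannot be computed, because the documents give no withdrawal rate by week. SAP Section 2.1 sends patients who complete the Week 144 or EOS visit to a Week 150 follow-up, which includes safety laboratory tests, but neither document says that a missed-dose withdrawal returns for it. The Week 96 and Week 102 labels may be left over from a shorter schedule; that is inference.

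**What to change.** **Protocol**

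- Reconcile Table 3-6 footnote 6 and Section 6.4 with Tables 3-2 and 3-4 and Sections 5.3.2 and 6.1 to 6.3, so that one Early Withdrawal rule covers every premature exit through the Week 150 visit.
- Reconcile Sections 4.4.1 and 4.4.2 with Section 6.4, so that missed-dose withdrawals have the same exit assessments collected as other withdrawals. The differing study drug rows must be reconciled too; that choice is the sponsor's.
- Reconcile the type of pregnancy test at EOS between Section 7.2.5 and the tables.
- Reconcile the Week 96 label in 6.4 and the Week 102 labels in 4.4.2 and 6.3.7 with the Week 144/EOS and Week 150 schedule.

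**SAP (shell clean-up)**

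- Use one EOS definition, Week 144 as in Section 3.3.1.
- Correct the footnotes to Listing 16.2.6.2 and the laboratory listing.
- Show Early Withdrawal and Week 150 records separately from the 144/EOS summaries.

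The cost is wording in both documents. The Early Withdrawal visit already exists, so the only added burden is that visit, with its laboratory tests, for patients who would otherwise have left without it.
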